7.1.1.1 Eligibility screening

After registering for Screening, patient eligibility will be checked once all screening procedures are completed.

7.1.1.2 Information to be collected on screening failures

Patients who sign an informed consent but fail to start treatment for any reason will be considered a screen failure. The reason for not being started on treatment will be entered on the Screening Log. The demographic information and Screening log pages in the eCRF must also be completed for Screen Failure patients. No other data will be entered into the clinical database for patients who are screen failures, unless the patient experienced a SAE during the Screening Phase (see Section 8 for SAE reporting details).

7.1.1.3 Patient demographics and other baseline characteristics

Data will be collected on patient characteristics including demographic information (age, sex, ethnicity, etc.) and other background or relevant medical history/current medical condition, transfusion history, disease history, prior chelation history, MDS classification using the revised International Prognostic Scoring System (IPSS-R), serum pregnancy test, vital signs at Visits 1 and/or 2.

To determine eligibility to be enrolled into the study, patients will also undergo assessments as per the inclusion and exclusion criteria which include hematology and biochemistry evaluations, hepatitis viral evaluation, serum creatinine and creatinine clearance, a known history of HIV positive test result (ELISA or Western blot) which is documented in the source documents, active Hepatitis B and/or C, serum pregnancy test and urinalysis.

Other assessments include chest X-ray (if clinically indicated), ocular examination, audiometry and electrocardiogram (ECG).

7.1.2 Run-in period

A washout period of 5 days is allowed for patients who completed CICL670F2201 and switched to commercially available DT or other iron chelation therapy. For details, refer Table 7-1.

7.1.3 Treatment period

The duration of study treatment in the current study is for a maximum of 24 months.

Treatment visits will commence at Visit 3 (Baseline). Patients will return to the site at 2 week intervals until Visit 5 (Month 1). Thereafter, scheduled visits will be monthly until EOT (Visit 28/Month 24).

Having completed the 24 weeks of CICL670F2201, patients recruited at Region Europe participating sites will be invited to continue FCT or switch from DT to the FCT formulation. Patients who completed CICL670F2201 but had switched to commercially available DT or other iron chelation will still be enrolled in the current study and receive FCT after a washout period.

All patients randomized in the DT arm in CICL670F2201 and well-managed on treatment with deferasirox DT will use an equivalent FCT dose. Patient switching from DT will use an equivalent FCT dose at the start of this study corresponding to their DT dose at the end of CICL670F2201 (see Appendix 14.2). A patient who is receiving an adjusted dose at the time of completing CICL670F2201 will commence this study receiving that adjusted dose until a time when it is deemed necessary to adjust the dose by the Investigator. Patients completing CICL670F2201 that had switched to commercially available DT or other ICT will have to undergo a 5-day washout period and then use an equivalent FCT starting dose corresponding to their pre-washout iron chelator dose.

Daily dose is calculated by the physician based on the patient's actual body weight.

For details on study design and dose adjustments, see Section 4 and Section 6.3. For details of assessments, see Table 7-1.

7.1.4 Discontinuation of study treatment

Patients may voluntarily discontinue from the study treatment for any reason at any time. If a patient decides to discontinue from the study treatment, the investigator should make a reasonable effort (e.g. telephone, e-mail, letter) to understand the primary reason for this decision and record this information in the patient's chart and on the appropriate eCRF

Page 43

pages. They may be considered withdrawn if they state an intention to withdraw, fail to return for visits, or become lost to follow-up for any other reason.

The investigator should discontinue study treatment for a given patient if, he/she believes that continuation would be detrimental to the patient's well-being.

Study treatment must be discontinued under the following circumstances:

- Pregnancy
- Unwillingness to comply with procedures as outlined in the study protocol, including unwillingness to comply with the prescribed study treatment
- Discovery of patient ineligibility
- Intake of prohibited medications
- AE(s)
- Abnormal laboratory value(s)
- Unsatisfactory therapeutic effect
- Protocol violation
- Subject withdrew consent
- Lost to follow-up
- Administrative problems
- Death

Patients who prematurely discontinue study treatment should undergo an EOT visit (Month 24) within 7 days from last dose, at which time all of the assessments listed for EOT visit will be performed.

7.1.5 Withdrawal of consent

Patients may voluntarily withdraw consent to participate in the study for any reason at any time. Withdrawal of consent occurs only when a patient does not want to participate in the study any longer, and does not want any further visits or assessments, and does not want any further study related contact.

Novartis will continue to retain and use all research results that have already been collected for the study evaluation. All biological samples that have already been collected may be retained and analyzed at a later date (or as required by local regulations).

If a patient withdraws consent, the investigator should make a reasonable effort (e.g. telephone, e-mail, letter) to understand the primary reason for this decision and record this information.

Study treatment must be discontinued and no further assessments conducted.

Further attempts to contact the patient are not allowed unless safety findings require communication or follow up.

7.1.6 Follow-up for safety evaluations

All patients must have safety evaluations for 30 days after the last dose of study treatment.

Data collected should be added to the AE eCRF and the Concomitant Medications eCRF.

7.1.7 Lost to follow-up

For patients whose status is unclear because they fail to appear for study visits without stating an intention to withdraw consent, the investigator should show "due diligence" by contacting the patient, family or family physician as agreed in the informed consent and by documenting in the source the steps taken to contact the patient, e.g. dates of telephone calls, registered letters, etc. A patient should not be considered lost to follow-up until due diligence has been completed. Patients lost to follow up should be recorded as such on the appropriate Disposition eCRF.

7.2 Assessment types

7.2.1 Efficacy assessments

Serum ferritin testing will be performed at Screening Visit 1 and 2. Following enrollment (Visit 3/Day 1) serum ferritin will be tested at 2 week intervals until Visit 5 (Month 1). Thereafter, scheduled testing will be monthly (refer Table 7-1). The Baseline serum ferritin value will be defined as the average of the 2 measurements obtained during the Screening period.

7.2.2 Safety and tolerability assessments

Safety will be monitored by assessing physical examination, vital signs and laboratory evaluations as well as collecting AEs at every visit. For details on AE collection and reporting refer to Section 8.

7.2.2.1 Physical examination

A physical examination will be performed at every visit. The physical examination at Visit 3 will serve as the Baseline physical examination for the entire study. The examination will entail an examination of general appearance, skin, neck (including thyroid), eyes, ears, nose, throat, lungs, heart, abdomen, back, lymph nodes, extremities and nervous system.

Information about the physical examination must be present in the source documentation at the study site.

Significant findings that were present prior to the signing of informed consent must be included in the Medical History page on the eCRF. Significant new findings that begin or worsen after informed consent must be recorded on the AE page of the eCRF.

7.2.2.2 Vital signs

Vital signs include blood pressure and pulse measurements and will be measured at all study visits. After the patient has been sitting for five minutes, with back supported and both feet placed on the floor, systolic and diastolic blood pressure will be measured 3 times using an automated validated device, e.g. OMRON, with an appropriately sized cuff. The repeat sitting measurements will be made at 1 - 2 minute intervals and the mean of the 3 measurements will be used. In case the cuff sizes available are not large enough for the patient's arm circumference, a sphygmomanometer with an appropriately sized cuff may be used.

7.2.2.3 Height and weight

Height will be measured at Screening.

Body weight (in indoor clothing, but without shoes) will be measured at Screening and at subsequent time points as specified in Table 7-1.

7.2.2.4 Auditory and ocular examination

Patients will undergo auditory and ocular examinations at Screening Visit 1 and at unscheduled visits (if needed) as described in the Table 7-1.

The auditory examination includes the following assessments:

- Comprehensive audiometry threshold examination
- Speech recognition

The ophthalmologic examination includes the following assessments:

- Visual acuity test
- Tonometry
- Slit lamp exam of anterior segment
- Slit lamp exam of the lens
- Fundoscopic and retinal examination

Information about the audiometry and ocular examinations must be present in the source documentation at study site. Significant findings of the audiometry and ocular examinations that meet the definition of an AE must be recorded in the AE summary page of the eCRF.

7.2.2.5 Laboratory evaluations

A local laboratory will be used for analysis of all specimens collected (Table 7-2).

Table 7-2 Local clinical laboratory parameters collection plan

Test Category	Test Name
Hematology	Hematocrit, Hemoglobin, Platelets, RBCs, White blood cells count with differential (Basophils, Eosinophils, Lymphocytes, Monocytes, Neutrophils), RBC Morphology
Biochemistry	Alkaline phosphatase, ALT/SGPT, AST/SGOT, Bicarbonate, Calcium, Chloride, Creatinine, inorganic phosphorus, potassium; sodium, total bilirubin, direct and indirect bilirubin*, BUN or CRP, serum ferritin
Urinalysis	Microscopic Panel** (RBCs, White Blood Cells, Casts, Crystals, Bacteria, Epithelial cells)
	Macroscopic Panel (Dipstick) (Bilirubin, Blood, Glucose, Ketones, Leukocytes esterase, Nitrite, pH, Protein, Specific Gravity, Urobilinogen)
Additional tests	Creatinine clearance, urine protein/creatinine ratio, serum pregnancy test, urine pregnancy test, hepatitis tests

RBCs = Red blood cells; WBCs = White blood cells; ALT/SGPT = alanine aminotransferase/serum glutamic pyruvic transaminase; AST/SGOT = Aspartate aminotransferase/serum glutamic oxaloacetic transaminase; BUN = Blood Urea Nitrogen; CRP = C-reactive protein.

^{*}Direct and indirect bilirubin assessment is only required if total bilirubin is > 1.5 ULN

Test Category Test Name

7.2.2.5.1 Hematology

Hematology samples will be collected at every visit as described in the visit evaluation schedule in Table 7-1.

Safety laboratory parameters monitored during the study will include hematocrit, hemoglobin, platelets, RBCs, white blood cells count with differential, RBC Morphology with differential (basophils, eosinophils, lymphocytes, monocytes, neutrophils).

7.2.2.5.2 Clinical chemistry

Clinical chemistry samples will be collected at every visit, as described in the visit evaluation schedule in Table 7-1.

Parameters to be measured will include: alkaline phosphatase, ALT/SGPT, AST/SGOT, bicarbonate, calcium, chloride, serum creatinine, inorganic phosphorus, potassium, sodium, total bilirubin (direct and indirect bilirubin only required if total bilirubin is >1.5 ULN), blood urea nitrogen (BUN) or urea, C-reactive protein (CRP). Also, serum ferritin level will be estimated from the blood serum (Section 7.2.1).

In accordance with the deferasirox label, serum creatinine, creatinine clearance, alkaline phosphatase, ALT/SGPT, AST/SGOT, direct bilirubin, indirect bilirubin, total bilirubin would have been assessed in duplicate before the initiation of therapy in the CICL670AIC04 study to establish a reliable pretreatment Baseline.

Creatinine clearance will be estimated using the Cockcroft-Gault equation or Schwartz formula for pediatric patients. This estimate will be provided each time serum creatinine is collected.

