7.1 Study flow and visit schedule

Table 7-1 lists all of the assessments and indicates with an "X", the visits when they are performed.

Patients should be seen for all visits to perform the scheduled assessments on the designated day, or as close to is as possible, i.e., not exceeding \pm 7 days. In this clinical trial, a week is 7 calendar days. Visits should be planned respective to Visit 3, rather than in relation to the previous visits.

All data obtained from these assessments must be supported in each patient's source documentation. No eCRF will be used as a source document. The table indicates which data are entered into the database (D) or remain in source documents only (S) (column category).

Table 7-1 Visit evaluation schedule

	Category	Protocol section	Screening	(z visits > 1week apart)¹							Tr	eatme	ent Pe	riod						End of Treatment	Safety Follow- up
Visit no.			1	2	3	4	5	6	7	8	9	10	11	12	13	14	15	16	17 to 27	28²	
Study month			-2	2W	D1	W2	M1	M2	М3	M4	М5	М6	М7	M8	M9	M10	M11	M12	M13 to M23	M24 or Within 7 days of last dose	30 days after last dose
Informed consent	(D)	7.1.1	Х																		
Inclusion/ exclusion criteria	(D)	7.1.1.1	Χ	Х																	
History of disease	(D)	7.1.1.3	Χ																		
Demography	(D)	7.1.1.3	Χ																		
Relevant medical history/current medical conditions	(D)	7.1.1.3	X																		
Prior chelation therapy	(D)	7.1.1.3	Х																		
Transfusion/RBC History	(D)	7.1.1.3	Х																		
Transfusions received	(D)	7.1.3	Х		Х	Х	Х	Х	Х	Х	Х	Х	Х	Х	Х	Х	Χ	Χ	Х	Х	
Physical exam	(S)	7.2.2.1	Х		Х	Χ	Х	Х	Х	Х	Х	Х	Х	Х	Х	Χ	Χ	Χ		Х	
Weight ³	(D)	7.2.2.3	Х		Χ	Χ	Х	Χ	Χ	Х	Х	Х	Х	Χ	Χ	Χ	Χ	Χ	Χ	Х	
Height	(D)	7.2.2.3	Х																		
Vital signs	(D)	7.2.2.2	Х	Х	Χ	Х	Х	Х	Х	Х	Х	Х	Х	Χ	Χ	Χ	Χ	Χ	Χ	Х	
Ocular exam⁴	(D)	7.2.2.4	Х															Χ		Х	
Audiometry ⁴	(D)	7.2.2.4	Х															Χ		Х	
ECG	(D)	7.2.2.7.1	Х															Х		Х	
Chest X-ray (if clinically indicated) ⁵	(D)	7.2.2.6	Х																		

	Category	Protocol section	Screening	apart)¹							Tı	eatme	ent Pe	riod						End of Treatment	Safety Follow- up
Visit no.		_	1	2	3	4	5	6	7	8	9	10	11	12	13	14	15	16	17 to 27	28 ²	
Study month			-2	2W	D1	W2	M1	M2	М3	M4	M5	М6	М7	M8	М9	M10	M11	M12	M13 to M23	M24 or Within 7 days of last dose	30 days after last dose
Prior and Concomitant medications	(D)	6.4	Х	х	х	х	Х	Х	Х	Х	Х	Х	Х	Х	Х	Х	х	Х	Х	Х	
Adverse events	(D)	7.2.2	Х	Х	Х	Χ	Х	Х	Х	Х	Х	Х	Х	Х	X	Χ	Х	Х	Х	Х	Х
Laboratory assessments ⁶ -Blood																					

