Hematology	(D)	7.2.2.5.1	Х	Х	Χ	Х	Х	Х	Х	Х	Х	Х	Х	Х	Χ	Х	Χ	Χ		Х	
Biochemistry	(D)	7.2.2.5.2	Χ	Х	Χ	Х	Х	Х	Х	Χ	Х	Х	Х	Х	Χ	Χ	Χ	Χ		Х	
Serum ferritin	(D)	7.2.1	Х	Х	Χ	Х	Х	Х	Х	Х	Х	Х	Х	Х	Χ	Χ	Χ	Χ	Х	Х	
Serum creatinine ⁷	(D)	7.2.2.5.2	Х	Х	Χ	Х	Х	Х	Х	Х	Х	Х	Х	Х	Χ	Χ	Χ	Χ	Х	Х	
Creatinine clearance	(D)	7.2.2.5.2	Х	Х	Χ	Х	Х	Х	Χ	Χ	Х	Χ	Х	Χ	Χ	Χ	Χ	Χ	Х	Х	
Hepatitis testing	(D)	7.2.2.5.5	Х																		
Serum pregnancy test	(D)	7.2.2.5.4	Х																		
Laboratory assessments- Urine																					
Urine dipstick	(D)	7.2.2.5.3	Х	Х	Χ	Х	Х	Х	Х	Х	Х	Х	Х	Х	Χ	Χ	Χ	Χ	Х	Х	
Microscopic urine ⁸	(D)	7.2.2.5.3	Х	Х	Х	Х	Х	Х	Х	Х	Х	Х	Х	Х	Χ	Х	Χ	Χ	Χ	Х	
Proteinuria ⁹ (urine protein/ creatinine ratio)	(D)	7.2.2.5.3	Х	Х	Х	Х	Х	Х	Х	Х	Х	Х	Х	Х	Х	х	Х	Х	Х	Х	
Urine pregnancy test ¹⁰	(D)	7.2.2.5.4			Χ															Х	
Study drug administration ¹¹	(D)								Dai	ily inta	ke of s	study c	drug fo	r up to	24 mont	hs					
Dispensed/returned FCT	(D)	6.1.1			Х	Χ	Χ	Χ	Χ	Χ	Х	Χ	Х	Х	Х	Х	Х	Х	Х	X	

	Category	Protocol section	Screening								Tr	eatme	ent Pe	riod						End of Treatment	Safety Follow- up
Visit no.			1	2	3	4	5	6	7	8	9	10	11	12	13	14	15	16	17 to 27	28²	
Study month			-2	w	D1	W2	М1	M2	М3	М4	M5	М6	М7	М8	М9	M10	M11	M12	M13 to M23	M24 or Within 7 days of last dose	30 days after last dose
count																					

Abbreviations: ECG=electrocardiogram; D=database; RBC=red blood cells; S=source documents

Note: Treatment and follow-up visits are scheduled relative to Visit 3 (Baseline visit).

¹Includes 5-day washout period for patients not continuing directly from CICL670F2201.

²End of Treatment visit will be undertaken for all patients completing the 24 months study, or discontinuing earlier for any reason.

³The dose of study medication will be adapted using Dosing Table (provided in Appendix 14.1) during the study if the change (increase or decrease) in body weight exceeds 10% of the body weight compared to the Visit 3 or the last dose adjustment due to change in patient's body weight.

⁴Not required if already performed within last 6 months and may be done additionally at discretion of investigator.

⁵An X-ray evaluation performed in the last 3 months before Screening Visit is acceptable.

⁶Refer to Table 7-2 for local laboratory parameters collection plan.

⁷Serum creatinine is assessed at Visit 1 and Visit 2 and their mean will be used to determine eligibility.

⁸Microscopic urine assessment is only required if positive urine dipstick (see Section 7.2.2.5.3).

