2.3.3.2 Laboratory data and vital signs

Laboratory data (biochemistry, hematology, and urinary parameters as well as serum creatinine, creatinine clearance, and proteinuria) and vital signs will be collected at screening visits, regular patient visits, and EOT.

If two or more assessments are performed within a time window then the assessment closest to the planned visit will be used in analyses by time window. When two values are equidistant from the planned assessment, the later one will be used in analyses.

Note: For worst post-baseline assessment, all on-treatment values are considered regardless of time windows. Table 2-2 shows the defined time windows, where a month is regarded as 4 weeks.

Table 2-2 Time windows for laboratory and vital signs data

Time window	Planned visit timing	Time window definition
On-treatment		
Baseline	On or before Study Day 1*	≤ Study Day 1*
Week 2	Study Day 15	Study Day 2 to Study Day 21
Month 1	Study Day 29	Study Day 22 to Study Day 43
Month 2	Study Day 57	Study Day 44 to Study Day 71
Month 3	Study Day 85	Study Day 72 to Study Day 99
Month 4	Study Day 113	Study Day 100 to Study Day 127
Month 5	Study Day 141	Study Day 128 to Study Day 155
Month 6	Study Day 169	Study Day 156 to Study Day 183
Month 7	Study Day 197	Study Day 184 to Study Day 211
Month 8	Study Day 225	Study Day 212 to Study Day 239
Month 9	Study Day 253	Study Day 240 to Study Day 267

Time window	Planned visit timing	Time window definition
Month 10	Study Day 281	Study Day 268 to Study Day 295
Month 11	Study Day 309	Study Day 296 to Study Day 323
Month 12	Study Day 337	Study Day 324 to Study Day 351
Month 13	Study Day 365	Study Day 352 to Study Day 379
Month 14	Study Day 393	Study Day 380 to Study Day 407
Month 15	Study Day 421	Study Day 408 to Study Day 435
Month 16	Study Day 449	Study Day 436 to Study Day 463
Month 17	Study Day 477	Study Day 464 to Study Day 491
Month 18	Study Day 505	Study Day 492 to Study Day 519
Month 19	Study Day 533	Study Day 520 to Study Day 547
Month 20	Study Day 561	Study Day 548 to Study Day 575
Month 21	Study Day 589	Study Day 576 to Study Day 603
Month 22	Study Day 617	Study Day 604 to Study Day 631
Month 23	Study Day 645	Study Day 632 to Study Day 659
Month 24	Study Day 673	Study Day 660 to Study Day 687
Month 25	Study Day 701	Study Day 688 to Study Day 715
Month 26	Study Day 729	Study Day 716 to Study Day 743
Month 27	Study Day 757	Study Day 744 to Study Day 771
Month 28	Study Day 785	≥ Study Day 772
EOT		

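### The protocol text puts hematology and chemistry at every visit, but Table 7-1 leaves them blank at Visits 17-27, so completers may have no scheduled ALT/AST or blood count between Month 12 and end of treatment.

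*Protocol*

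**What the plan says.** Four protocol sections place these assessments at every visit:

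- 7.2.2: "Safety will be monitored by assessing physical examination, vital signs and laboratory evaluations as well as collecting AEs at every visit".
- 7.2.2.1: "A physical examination will be performed at every visit".
- 7.2.2.5.1: "Hematology samples will be collected at every visit as described in the visit evaluation schedule in Table 7-1".
- 7.2.2.5.2: "Clinical chemistry samples will be collected at every visit, as described in the visit evaluation schedule in Table 7-1".

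Protocol 7.1.3 makes visits monthly from Month 1 to Visit 28 (Month 24). SAP 2.3.3.2 agrees with the text: laboratory data, with biochemistry and hematology named, "will be collected at screening visits, regular patient visits, and EOT". SAP Table 2-2 then gives a monthly analysis window for each of Months 13-23.

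Table 7-1, where an X marks each visit at which an assessment is done, differs. Hematology and biochemistry are marked at Visits 1-16 and 28. Physical examination is marked at Visits 1, 3-16 and 28. All three rows are blank in the column for Visits 17-27. Ferritin, serum creatinine, creatinine clearance, urine tests, weight, vital signs and adverse events are all marked in that column.

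**The concern.** Sections 7.2.2.5.1 and 7.2.2.5.2 refer the reader to Table 7-1, so sites may well follow the table. A completer would then have no scheduled transaminase or blood count between Month 12 and the end-of-treatment visit, when dosing stops.

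**Monitoring.** Protocol 6.3.1.6 acts on a persistent and progressive transaminase rise, which can only be recognised from serial values. Protocol 6.3.1.9 asks for regular blood counts. A lasting abnormality would be found at end of treatment, too late to guide dosing. Safety is the primary objective, and Protocol 8.6 provides no data monitoring committee.

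**Analysis.** The by-visit summaries and mean/SE plots for Months 13-23 would hold only unscheduled ALT, AST, RBC, platelet and WBC values. The worst-value shift tables could miss an abnormality that starts and resolves inside the gap, and a reader could take a lack of testing for a lack of abnormality.

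**Working it through.** The plan gives no figure of its own to reproduce. The check has three parts: reading the schedule, counting samples, and working out what a gap of that length does to detection.

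**1. Is the blank real?** Each Table 7-1 row checked has the same number of fields as the visit header. Hematology and biochemistry are empty only at Visits 17-27. Ferritin, serum creatinine and creatinine clearance have no empty cell from Visit 1 to Visit 28. A conversion fault is therefore unlikely. Urinalysis (7.2.2.5.3) also says every visit with a reference to Table 7-1, and its rows are marked at Visits 17-27. Physical examination is also blank at Visit 2.

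**2. Scheduled panels per completer, from Visit 3**

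| | Text | Table 7-1 |
|---|---|---|
| Visits 3-28 | 28 − 3 + 1 = 26 | 14 (Visits 3-16) + 1 (Visit 28) = 15 |
| After Month 12 (Visits 17-28) | 12 | 1 |

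The difference is 11 visits (27 − 17 + 1).

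**3. Length of the gap.** SAP Table 2-2 puts Month 12 at Day 337 and Month 24 at Day 673: 673 − 337 = 336 days. Protocol 7.1 allows ±7 days at each visit, giving 322 to 350 days. In calendar months the gap is about 365 days.

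**4. Outputs affected in the second year.** SAP 2.6.2 plots 7 laboratory parameters over time. Taking away serum creatinine and creatinine clearance leaves 5 affected: ALT, AST, RBC, platelets and WBC. Protocol Table 10-1 has 6 notable-range rows. Taking away serum creatinine, creatinine clearance and urine protein/creatinine ratio leaves 3 affected: platelets, neutrophils and ALT/AST.

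**5. Delay for a persistent abnormality.** With onset uniform over the gap, the mean delay to the next scheduled value is gap/2. Under the table this is 336/2 = 168 days (maximum 336). With monthly panels it is 28/2 = 14 days (maximum 28).

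**6. Chance of seeing a transient abnormality.** With uniform onset, the proportion seen is min(1, duration/interval between tests). The durations and the unscheduled-test frequencies are assumptions, because the documents give neither.

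| Interval between tests | 28 days' duration | 56 days' duration | 84 days' duration |
|---|---|---|---|
| 336 days (table, no unscheduled test) | 28/336 = 8% | 56/336 = 17% | 84/336 = 25% |
| 365 days (same, calendar months) | 8% | 15% | 23% |
| 168 days (one recorded test mid-gap) | 17% | 33% | 50% |
| 84 days | 33% | 67% | 100% |
| 28 days (text) | 100% | 100% | 100% |

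**The case against.** The strongest reply is that the table governs and a lighter second year was meant. Both laboratory sentences defer to Table 7-1. The table keeps the renal, urine and ferritin tests while dropping others, which looks deliberate, and Protocol 2.2 speaks of less frequent monitoring. The SAP sentence and windows cover all laboratory data together, so they do not prove that monthly ALT/AST was expected. This reading is plausible, but no text states a reduced schedule. Four protocol sections and the SAP sentence would then need correcting.

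The second reply is that the effect is limited. This stands in part:

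- The primary laboratory variables in SAP 2.6.1 are changes at Months 6 and 12. The second-year tables are descriptive, and thin windows would show in the reported n.
- Early discontinuers have an end-of-treatment panel within 7 days of last dose.
- Unscheduled results count: "For worst post-baseline assessment, all on-treatment values are considered regardless of time windows", and SAP 2.9.3 repeats this for abnormal values.
- Transfusing to a hemoglobin of at least 9 g/dL (6.4.2) implies some routine blood counts, so a year without any is unlikely for hematology. However, Protocol 4.1 says other assessments done as standard of care are not captured in the eCRF, so such results may not reach the analysis.
- Sections 6.3.2 and 8.1.2.1 require follow-up of abnormal laboratory values, but only once they have been found. They do not cover silent onset after Month 12. Under 8.1.1, a silent laboratory abnormality becomes an adverse event only after someone measures it and judges it significant.

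The detection percentages do rest on assumed durations and uniform onset. They show the range of possible loss and do not forecast it.

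**Conclusion.** The concern holds. The text and Table 7-1 conflict on hematology, chemistry and physical examination at 11 of the 26 visits from Visit 3 to Visit 28. This is certain from the documents. The consequence is conditional: if sites follow the table, completers have 1 scheduled panel after Month 12 instead of 12, and a 336-day gap in ALT/AST and blood counts.

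How many abnormalities would be missed depends on unscheduled testing, which the documents do not quantify. For durations of 4, 8 and 12 weeks, the proportion seen runs from 8%, 17% and 25% with no such test to 33%, 67% and 100% with a recorded test every 84 days. The point should be fixed, because safety is the primary objective and the dose rules for liver enzymes and cytopenias depend on serial values. It does not threaten the Month 6 and 12 laboratory results, the renal data or the ferritin analysis.

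**What to change.** **Preferred.** Mark hematology and biochemistry at Visits 17-27 in Table 7-1, and bring the physical examination row and section 7.2.2.1 into agreement (including Visit 2). Blood is already drawn at those visits for ferritin and creatinine, so no visit or venepuncture is added. The cost is up to 11 extra local panels of each type per completer, at most 11 × 58 = 638 of each if all 58 patients planned in SAP section 3 complete. The documents give no unit cost; it is assumed to be small.

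**If the reduced schedule was intended.** Correct the every-visit wording in 7.2.2, 7.2.2.1, 7.2.2.5.1 and 7.2.2.5.2, and the sentence on regular visits in SAP 2.3.3.2. This costs text only.

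**In that case, and for any patient already past Month 12.** Present second-year ALT/AST and blood-count shifts with the number of patients actually tested after Month 12 as the stated denominator.
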